8.2 Interim Analyses and Stopping Rules

A stopping rule for safety will halt accrual to the study and prompt reevaluation of the regimen if unacceptable treatment-related toxicity (defined as any Grade 4 toxicity, any recurrent Grade 3 toxicity, or any Grade 3 toxicity persisting more than 2 weeks), or treatment-related delay in cystectomy beyond 12 weeks (including both the treatment period and any delay due to an adverse event), is observed at a frequency of $\geq 33.3\%$

No formal interim stopping rule for efficacy will be performed. This is due to the fact that immune therapies may require weeks to months to have efficacy, and therefore the true antitumor activity of atezolizumab and tiragolumab may not be apparent at the time of cystectomy. Rather, durable immune responses may be generated against the tumor and may prevent post-cystectomy recurrence; this effect may not be detectable for months to years after study drug administration.

Furthermore, given the relatively small sample size of this study an interim stopping rule for futility based on longer-term clinical endpoints (i.e. relapse-free survival) is not considered feasible or warranted.

8.3 Analysis Plans

8.3.1 Analysis Population

All patients who receive any part of a dose of any study drug will be analyzed for safety and efficacy. Subjects who discontinue from study participation prior to receiving any dose of study therapy may be replaced after discussion with the Study Chair. Subjects who have received any dose of study therapy will not be replaced.

Demographic and baseline characteristics will be summarized. In general, frequency distribution and percentage will be used to summarize categorical measurements, while mean with standard deviation and median with range will be used to describe symmetric and skewed continuous measurements, respectively. Univariate analysis among variables will be assessed using the two-sample t-test, Wilcoxon-rank-sum test, Chi-square test, as appropriate.

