 - **Dose Level 1** (Atezolizumab 1200 mg x 3 cycles, Tiragolumab 600 mg x 3 cycles): There will be an initial safety lead in of 6 patients treated with this regimen, at which time enrollment will pause to assess the safety of this combination treatment. As long as no more than 1 out of the initial 6 patients experience dose limiting toxicities (DLTs) or a delay in the time to radical cystectomy, the remaining patients will enroll at the same dose and regimen.
 - If two or more patients out of the initial six experience DLTs within the first cycle (3 weeks), accrual will be halted and the combination reevaluated.
 - If two or more patients out of the initial six experience DLTs within the first 2 cycles (6 weeks), accrual to this dose level will be halted and we will move to dose level 3.
 - If two or more patients out of the initial six experience DLTs or delay in the time to radical cystectomy, and no more than 1 patient experienced DLTs during the first 2 cycles (6 weeks), the next six patients will be treated at dose level 2
 - **Dose Level 2** (Atezolizumab 1200 mg x 3 cycles, Tiragolumab 600 mg x 2 cycles): As long as no more than 1 out of 6 patients experience DLTs or a delay in the time to radical cystectomy with this treatment, the remaining patients will enroll at the same dose and regimen.
 - If two or more patients out of the six patients experience DLTs within the first cycle (3 weeks), accrual will be halted and the combination reevaluated.
 - If two or more patients out of the six experience DLTs or delay in the time to radical cystectomy, and no more than 1 patient experienced DLTs during the first cycle (3 weeks), the next six patients will be treated at dose level 3
 - **Dose Level 3** (Atezolizumab 1200 mg x 3 cycles, Tiragolumab 600 mg x 1 cycle): This will be the selected regimen if no more than 1 out of 6 patients experience DLTs or a delay in the time to radical cystectomy. However if 2 or more patients experience DLTs or a delay in the time to radical cystectomy with this combination regimen, then accrual will be halted and the combination reevaluated.
- Expansion: Once the intended treatment regimen is established following completion of the safety assessment, an additional 15 patients will be enrolled at the same regimen for a total of 21 patients on that treatment regimen.

Cohort B Safety Lead-in Schema

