5.4 Dose Limiting Toxicities (DLTs)

Dose Limiting Toxicity (DLT) is an unacceptable treatment-related toxicity that occurs between time of first dose and time of cystectomy, defined as:

- any Grade 4 toxicity, or
- any recurrent Grade 3 toxicity, or
- any Grade 3 toxicity persisting more than 2 weeks, or
- any toxicity that results in delay of cystectomy beyond 12 weeks from the first dose of study drug

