7.1.2.1 Definitions

Evaluable for toxicity

All patients will be evaluable for toxicity from the time of their first treatment with the study drug.

Evaluable for objective response

Only those patients who have measurable disease present at baseline, have received at least one cycle of therapy, and have had their disease re-evaluated prior to resection will be considered evaluable for response. These patients will have their response classified according to the definitions stated below. (Note: Patients who exhibit objective disease progression prior to the end of Cycle 1 will also be considered evaluable.)

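### The Cohort B lead-in has no definition of a DLT-evaluable patient, so the three- or two-dose tiragolumab level can be cleared on fewer than six informative patients

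*Combined protocol and SAP*

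**What the plan says.** **Replacement.** Section 8.3.1 allows replacement before dosing: "Subjects who discontinue from study participation prior to receiving any dose of study therapy may be replaced after discussion with the Study Chair". After dosing it does not: "Subjects who have received any dose of study therapy will not be replaced". Section 6.9.7 repeats the bar for patients who withdraw after a dose, and adds that nobody is followed once consent is withdrawn.

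**Evaluability.** Section 7.1.2.1 says "All patients will be evaluable for toxicity from the time of their first treatment with the study drug". Section 5.7.2 likewise treats each patient given study drug as evaluable for safety. Neither sets a minimum exposure or follow-up. By contrast, sections 7.1.1 and 7.1.2.1 do set conditions for pathologic and objective response.

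**Lead-in decision.** Section 3.1 gives each level six patients and clears it on at most one event. For Dose Level 2 the wording is "As long as no more than 1 out of 6 patients experience DLTs or a delay in the time to radical cystectomy with this treatment"; Levels 1 and 3 have the same threshold. Table 5.3 shows that the levels differ only in the number of tiragolumab doses: three, two or one.

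**Window and timing.** Section 5.4 defines a DLT as "an unacceptable treatment-related toxicity that occurs between time of first dose and time of cystectomy". Section 5.5 nevertheless sets the safety review for when all six are accrued and have had at least one dose.

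**The concern.** The lead-in decides how many tiragolumab doses the 15 expansion patients receive before curative-intent surgery. The count is informative about a three- or two-dose level only for patients who received enough of that regimen, and were observed long enough, for its toxicity to show.

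Section 3.4 lists ways off treatment that need not involve a DLT: progression, intercurrent illness, withdrawal and non-compliance. Suppose a patient receives one dose of each drug and then leaves by one of these routes. Under the replacement and evaluability rules nobody takes that place and the patient remains toxicity-evaluable. If the tally is simply events out of six, the patient enters it as a non-event.

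The effect runs in one direction: it makes a level more likely to clear, including one whose true toxicity is at the rate the protocol calls unacceptable. Non-replacement suits the safety and efficacy analysis sets. The difficulty is that nothing separates those sets from the denominator of the dose-level decision.

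**Working it through.** **Inputs from the documents.** Six patients per level, cleared on at most one event (3.1). Unacceptable frequency of 33.3% or more (5.5, 8.2).

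**Assumptions.** The documents give no early-departure rate, so 5% to 10% per patient is assumed, with 20% as an upper illustration. The DLT risk of an early leaver is not given either. It is taken as zero (no information) or one third of the full risk.

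**Step 1: the plan's own figure.** The smallest count that fails a level is 2 of 6 = 33.3%, which matches the stated threshold.

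**Step 2: chance of clearing with m informative patients and true DLT rate p.**

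P(clear) = (1 − p)^m + m·p·(1 − p)^(m−1)

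At p = 1/3:
- m = 6: 0.088 + 0.263 = 0.351
- m = 5: 0.132 + 0.329 = 0.461
- m = 4: 0.198 + 0.395 = 0.593

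| True DLT rate | 6 informative | 5 | 4 | 3 |
|---|---|---|---|---|
| 20% | 0.655 | 0.737 | 0.819 | 0.896 |
| 33.3% | 0.351 | 0.461 | 0.593 | 0.741 |
| 40% | 0.233 | 0.337 | 0.475 | 0.648 |
| 50% | 0.109 | 0.188 | 0.312 | 0.500 |

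With three informative patients and one DLT, the rate among the informative is 1/3 = 33.3%. That is already at the stopping threshold, yet the tally reads 1 of 6.

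**Step 3: leavers with partial risk.** Give each leaver one third of the full risk, 1/3 × 1/3 = 1/9.
- One leaver, no event: (2/3)^5 × 8/9 = 0.117.
- One leaver, exactly one event: 5 × (1/3) × (2/3)^4 × (8/9) + (2/3)^5 × (1/9) = 0.307.
- Sum for one leaver: 0.424. The same calculation for two leavers gives 0.507.

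**Step 4: how often leavers occur.** The chance that at least one of six leaves is 1 − (1 − d)^6: 26% at d = 5%, 47% at 10% and 74% at 20%. The chance of two or more is 3% at 5% and 11% at 10%.

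**Step 5: average effect.** Suppose each patient leaves with probability d, independently of DLT risk, and carries a fraction f of the full risk if so. The effective rate per patient is q = p·(1 − d + d·f), and P(clear) = (1 − q)^6 + 6q(1 − q)^5. At p = 1/3, against 35.1% with no leavers:

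| d | f = 0 | f = 1/3 |
|---|---|---|
| 5% | 38.5% | 37.3% |
| 10% | 42.0% | 39.6% |
| 20% | 49% | 44% |

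For d of 5% to 10% the rise is therefore about 2 to 7 points.

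**The case against.** **The text does not say that a leaver counts as clean.** Correct. A reader might infer that the protocol orders this, but it does not. Section 3.1 speaks of six patients treated with the regimen, which could be read as excluding someone who had one dose of three. Counting the leaver is an inference from the replacement rule, the evaluability rule, the one-dose trigger in 5.5 and the absence of any other definition. What stands is that the documents allow that reading and offer nothing to settle it.

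**Clearance is not the last safeguard.** Also correct. A reader might infer that a wrongly cleared level then runs unchecked through 15 more patients. Sections 5.5 and 8.2 keep the 33.3% stopping rule in force, and 5.5 provides for ongoing review. Appendix 2 requires DSMC authorization before expansion, on a report of AEs, SAEs and DLTs, and the DSMC Chair or designee can ask for more information. These limit the harm. But the ongoing rule acts only after expansion patients have been exposed. The Appendix 2 audit of lead-in visits covers the first cycle only. Neither sets an evaluability rule for the lead-in decision.

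**Leavers are not wholly uninformative.** Only withdrawal of consent ends all follow-up. Patients who stop drug for other reasons remain under adverse-event reporting for 30 days after the last dose, and attributed SAEs are reported after that (5.7.2, 7.4). This is why the one-third-risk figures are shown. Such follow-up still informs on the exposure received, not on the assigned two or three doses.

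**Conclusion.** The point holds as a gap in the lead-in decision rule. As written, tiragolumab x 3 or x 2 can be cleared on fewer than six informative patients. At a true DLT rate of 33.3%, the chance of clearing rises from 35% to 46% with one uninformative leaver and 59% with two. With one third of the risk per leaver, it rises to 42% and 51%.

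It would be too strong to read 46% or 59% as the expected error rate. Those figures are conditional on leavers having occurred and having given no DLT information. Averaged over an assumed 5% to 10% departure rate, the rise is about 2 to 7 points.

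The size rests on the assumed departure rate and residual risk, and on departures being unrelated to DLT risk. A patient who leaves because of a qualifying toxicity already counts as a DLT and is outside the point. Dose Level 3 is also outside the claim, because one dose is its full tiragolumab exposure. The planned 21 patients and the no-replacement rule for the safety and efficacy analyses are not in question.

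**What to change.** Keep no-replacement for every safety and efficacy analysis. For the lead-in decision only:

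1. In 3.1, apply the at-most-one-in-six rule to six DLT-evaluable patients. These are patients who had a DLT or a treatment-related surgery delay, or who completed the DLT window with the exposure that the sponsor specifies as sufficient to judge that level. The exposure requirement is a clinical matter for the sponsor.
2. State how a patient stopped for a toxicity short of a DLT is classified, so that such a patient is not dropped as uninformative. For example, a Grade 3 hepatic event calls for permanent discontinuation in 5.7.4.2. If it resolves within two weeks, does not recur and does not delay surgery, it does not meet the DLT definition in 5.4.
3. Let a non-evaluable patient be followed in the tally by the next patient enrolled at that level, who uses one of the 15 expansion slots. The total stays at 21 if the level clears, and the non-evaluable patient remains in all analyses.
4. Reconcile 3.1, 5.5, 7.1.2.1 and 8.3.1 with this definition, including the one-dose trigger for the safety review. Section 6.9.7 needs no change if the exception is confined to the tally.

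**Cost.** The enrolment pause may lengthen by up to one DLT window, about 12 weeks. If a level fails, there may be one extra patient per non-evaluable patient, with a conforming edit to the 6–18 lead-in range and the 33-patient maximum in the Abstract and 3.2.

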8.3.2 Analysis of Primary Endpoints

The immunologic effect of activity study therapy within bladder tissue will be measured by a change in the CD3⁺ T cell count/ μm^2 between the pretreatment biopsy and the cystectomy tissue following study therapy administrations. Immunohistochemistry will be performed in the [name] lab at UCSF per established SOPs. Based on prior experience tissue will be designated into 3 distinct compartments: benign epithelium, tumor centers, and tumor interfaces. Tumor interfaces will be defined as fields where malignant and benign epithelium are present. Automatic cell counts for single- and double-stained cells will be determined for each field with color-specific algorithms.

The cell count for each compartment will be reported as the mean for each of the five quantitated fields. Cells of interest will include CD3⁺ T cells, CD3⁺ Ki67⁺ proliferative T cells,

CD4+ FoxP3- helper T cells, CD4+ FoxP3+ regulatory T cells, CD8+ cytotoxic T cells, as well as PD-1 expression on the different lymphocytes. In collaboration with Genentech, PD-L1 expression on both tumor and immune cells within the microenvironment will be assessed.

For each cohort, the change of T cell counts from pre-treatment to post-treatment will be calculated for each compartment as log2 of the ratio of post-treatment vs. pre-treatment counts. If different regimens are used (for example atezolizumab x 3 doses and tiragolumab x 2 doses) two-sample Wilcoxon rank sum test will be used to compare the difference of the change from pretreatment to post-treatment between cohorts to assess if the intratumoral immune response associated with increasing numbers of treatments. No multiple comparison adjustments will be performed.

8.3.2.1 pT0 rate

Point estimates and 95% confidence intervals of pathologic T0 rate at the time of cystectomy as defined in Section 7.1.1 will be obtained for subjects treated with atezolizumab and tiragolumab. Pathologic T0 rate at the time of cystectomy will be compared with the null hypothesis rate (see Section 8.1) separately by using one-sample proportion test.

8.3.2.2 Safety

Adverse events occurring prior to surgery will be summarized by maximum toxicity grade for all patients treated with the particular regimen. The toxicity grade for laboratory data will be calculated using NCI CTCAE-v4.0 for the (already accrued) Cohort A and using CTCAE-v5.0 for Cohort B, and the lab data will be summarized according to the subjects' baseline grade and maximum grade for each cycle of therapy. The percentage of subjects requiring a treatment-related delay in surgery beyond 12 weeks from study start will be summarized using descriptive statistics. All treatment related adverse events that lead to delay in cystectomy will be graded using NCI CTAE-v4.0 or 5.0 as discussed above and will be recorded.

8.3.3 Analysis of Secondary Endpoints

8.3.3.1 Near complete pathologic response rate, 2 year relapse-free survival, 2 year overall survival

Point estimates and 95% confidence intervals of the near complete pathologic response rate, defined as the presence of only pTa or pTis in patients with T2 or greater disease at baseline, the 2 year RFS rate defined from study start until recurrence of disease or death from any cause, and the 2 year overall survival (OS) rate defined from study start until death from any cause, will be obtained for patients enrolled in the study, and compared with the null hypothesis rate (see Section 8.1) separately by using one-sample proportion test. RFS and OS will be obtained by Kaplan Meier method for the ITT population.

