Exploratory Objectives	
Cohorts A & B
 
 1. To define the immunologic infiltration within bladder tissue following administration of neoadjuvant combination treatment with atezolizumab and tiragolumab when compared to pre-treatment TURBT biopsies 2. To assess the immunologic impact of combined tiragolumab and atezolizumab regimen in the urothelial cancer tumor microenvironment (Cohort B) in comparison to the impact on the tumor microenvironment of atezolizumab monotherapy in a similar cohort of patients treated with neoadjuvant atezolizumab for MIBC at UCSF (Cohort A) 3. To assess for tumor-based biomarkers of response and resistance to this combination therapy using single-cell RNA sequencing (scRNA-seq) and high-dimensional flow cytometry 4. To define the treatment-induced effects on circulating immune cells with this combination therapy 5. To assess the presence of antigen-specific immune responses to a broad panel of candidate tumor antigens
Sample Size	
Cohort A Safety Lead-In: 18 participants (already accrued as of October 2020)
 
Cohort A Expansion: Up to 9 additional participants may be accrued so that Cohort A expansion group = up to 15 total participants treated at established regimen (6 participants treated at highest administered dose from multi-dose portion + up to 9 additional participants).
 
Cohort B Safety Lead-In: 6-18 patients will be included.
 
Cohort B Expansion: 15 additional patients treated with the regimen established during the safety lead-in phase (21 total treated with established regimen)
 
Total Cohort A accrual: Up to 27 patients
 
Total Cohort B accrual: 21-33 patients

Duration of Study Treatment	9 weeks

Duration of Follow up	2 years
Safety Assessments	For Cohort A: Frequency of all grade treatment-related toxicities according to NCI CTCAE v4.0 For Cohort B: Frequency of all grade treatment-related toxicities according to NCI CTCAE v5.0
Efficacy Assessments	Pathologic complete response rate (pT0N0), pathologic partial response rate (<pT2N0), median relapse-free survival and overall survival, 2 year relapse-free survival rate and overall survival rate

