A similarly designed study, the PURE-01 trial²⁰, also accrued patients with MIBC to receive neoadjuvant PD-1 checkpoint inhibition. Patients had a predominant urothelial carcinoma histology and clinical (c)T≤3bN0 stage tumor. They received three cycles of pembrolizumab (a PD-1 inhibitor) 200 mg every 3 weeks before RC. The primary end point in the intention-to-treat population was pathologic complete response (pT0). Biomarker analyses included programmed death-ligand 1 (PD-L1) expression using the combined positive score (CPS; Dako 22C3 pharmDx assay), genomic sequencing, and an immune gene expression assay. Fifty patients were enrolled from February 2017 to March 2018. Twenty-seven patients (54%) had cT3 tumor, 21 (42%) cT2 tumor, and two (4%) cT2-3N1 tumor. One patient (2%) experienced a grade 3 transaminase increase and discontinued pembrolizumab. All patients underwent RC; there were 21 patients with pT0 (42%; 95% CI, 28.2% to 56.8%). As a secondary end point, downstaging to <pT2 was achieved in 27 patients (54%; 95% CI, 39.3% to 68.2%). In 54.3% of patients with PD-L1 CPS ≥ 10% (n = 35), RC indicated pT0, whereas RC indicated pT0 in only 13.3% of those with CPS < 10% (n = 15). A significant nonlinear association between tumor mutation burden (TMB) and pT0 was observed, with a cutoff at 15 mutations/Mb. Expression of several genes in pretherapy lesions was significantly different between pT0 and non-pT0 cohorts. Significant post-therapy changes in the TMB and evidence of adaptive mechanisms of immune resistance were observed in residual tumors.

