2.2 Secondary Objective(s) and Endpoint(s)

Cohorts A and B

Multi-Dose Cohorts

1. To evaluate the safety and feasibility of administering up to 3 cycles of Atezolizumab pre-operatively to patients with resectable urothelial bladder cancer. Note this is the coprimary objective for Cohort B.
 - Endpoint: The percentage of patients with treatment-related adverse events according to CTCAE v5.0 or treatment-related delays in surgery beyond 12 weeks following administration of neoadjuvant treatment with atezolizumab with or without tiragolumab. Note for Cohort A CTCAE v4.0 was used.

Expansion Cohorts

1. To assess the anti-tumor activity of neoadjuvant treatment as determined by pathologic partial response (<pT2N0) assessed at the time of radical cystectomy
 - Endpoint: Percentage of patients with pathologic downstaging (<pT2N0) at the time of radical cystectomy
2. To determine the 2-year relapse-free survival (RFS) rate and median RFS from time of radical cystectomy in patients treated with neoadjuvant therapy
 - Endpoint: 2-year RFS rate and median RFS in ITT population
3. To determine the 2-year overall survival (OS) and median OS from time of radical cystectomy in patients treated with neoadjuvant therapy
 - Endpoint: 2-year OS rate and median OS in ITT population
4. To assess the intratumoral immune response of neoadjuvant by comparing pre-treatment TURBT with post-treatment cystectomy tumor specimens

- Endpoint: Association of tumor and T-cell PD-L1/PD-1 immunohistochemical expression with disease response

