7.1 Evaluation of Efficacy

7.1.1 Pathologic Response

Treatment efficacy will be determined by the pathologic determination of tumor response at the time of cystectomy. This will include determination of tumor response in the bladder as well as in any resected lymph nodes.

Pathologic determination should be in accord with collaborative guidelines³³ and should specifically proceed as follows:

For all cystectomy specimens the pathologist will cut the tissue at roughly 0.5cm intervals to look for a tumor mass. If no tumor mass is seen on gross examination then representative sections should be put in. If cystoscopic abnormalities are noted by the treating Urologist, then the treating Urologist will indicate location of cystoscopic abnormalities (up to 4 different ones) on the pathology requisition, and that pathologists will "block in" each of these areas (up to 4 different areas) during pathologic evaluation of the bladder to cover at least 1 cm square area of each indicated location. This is in addition to any grossly-recognized residual tumor foci that are seen when opening the bladder for pathologic evaluation.

It is similarly recommended that prior surgical sites or mucosal ulcerations be sampled in their entirety for residual tumor and adequate mapping performed. Furthermore, areas that appear red and regions of mucosal induration should be sampled to rule out CIS. There is no need for complete embedding of the entire bladder wall. Communication between the urologic surgeon and pathologist is key in cases where prior surgical sites, mucosal ulcerations, or alterations are not evident to ensure that appropriate tissue sampling occurs.

The following definitions apply to determination of pathologic responses:

Evaluable for pathologic complete response

Only those patients who have received at least one cycle of therapy, and have had their disease evaluated pathologically at the time of resection will be considered evaluable for pathologic response. These patients will have their response classified according to the pathologic complete response definitions below:

- **Pathologic complete response (pCR):** Defined as the presence of pT0 disease. Similarly there must be no evidence of tumor in all resected lymph nodes (N0).

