- **Near pathologic complete response (near pCR):** Defined as the presence of Ta or Tis disease (or both) in the resection specimen, without evidence of any higher stage disease elsewhere or evidence of tumor in all resected lymph nodes (N0).

All patients will be followed for 2 years post-cystectomy to evaluate for tumor recurrence.

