8.1 Determination of Sample Size and Power Calculation

Cohort A

Multi-dose phase: With 6 patients in each cohort, there will be 80% of power to detect the effect size of 1.5 at significance level of 0.1. For the lowest dose level, a 2-fold increase from pre-treatment to post- treatment is expected, if at the higher dose level, there is more than 3-fold increase, assuming the standard deviation equals 1, then there will be 80% power to detect significant treatment effect on the intratumoral immune response.

Expansion phase: Data from a study of intravesical valrubicin chemotherapy in BCG refractory patients³⁴ demonstrated that a 21% CR rate is achievable at 6 months. Assuming a 5% (null) CR rate for untreated patients at 6 months, 15 patients would be required to observe an improvement to a 36% CR rate at 6 months in response to-PD-L1 therapy (effect size = 0.642), at a significance level of 0.1 with 80% power.

Cohort B

A pT0 rate at cystectomy was observed for ~30% of patients treated with immune checkpoint inhibitors monotherapy based on published Phase II clinical trials. In order to observe an improvement from a 30% CR rate (null hypothesis) to 60% CR rate (alternative hypothesis) with the combination of atezolizumab and tiragolumab a total of 21 patients are required in Cohort B assuming a significance level of 0.05 and 80% power.

Using these assumptions, following a lead in safety phase of 6 patients at a combination regimen that is deemed to be safe based on the criteria outlined above, a further 15 patients will be enrolled at the same regimen. This will make a total of 21 patients to be treated in Cohort B with the intended regimen.

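### The declared secondary response endpoint (<pT2N0) has no planned analysis: Section 8.3.3.1 analyses near pCR (Ta/Tis only) instead, and pT1N0 falls in neither planned rate

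*Combined protocol and SAP*

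**What the plan says.** **Declared endpoint.** Section 2.2, first expansion-cohort secondary objective: "Endpoint: Percentage of patients with pathologic downstaging (<pT2N0) at the time of radical cystectomy". The Abstract lists the same quantity among the efficacy assessments as the "pathologic partial response rate (<pT2N0").

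**Pathology definitions.** Section 7.1.1 defines two response classes. Pathologic complete response is "Defined as the presence of pT0 disease", with negative nodes. Near pathologic complete response is "Defined as the presence of Ta or Tis disease (or both) in the resection specimen, without evidence of any higher stage disease elsewhere", also with negative nodes. There is no <pT2N0 or partial-response class.

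**Analysis.** Section 8.3.3.1 gives a point estimate and 95% CI for the near complete response rate, "defined as the presence of only pTa or pTis in patients with T2 or greater disease at baseline". That rate is then to be "compared with the null hypothesis rate (see Section 8.1) separately by using one-sample proportion test". Section 8.1 sets a null only for complete response; for Cohort B it reads "In order to observe an improvement from a 30% CR rate (null hypothesis) to 60% CR rate (alternative hypothesis"). Section 8.3.2.1 analyses the pT0 rate as the primary endpoint.

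**The concern.** The endpoint and the analysed rate are different sets of patients, not two labels for one set. Followed literally, the plan never estimates the first-listed expansion secondary endpoint and reports a narrower rate in its place. The stage data to compute either rate will exist. In an open-label single-arm study, the choice between two very different response rates would therefore be made after the results are known.

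The substituted rate is also harder to interpret. A patient who improves from residual Ta/Tis to T0 leaves its numerator, so it does not move in one direction with benefit. The <pT2N0 rate does not have this defect.

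**Working it through.** **1. The plan's own figure.** The only powered response figure is N = 21 for the Cohort B pT0 rate, 30% against 60%, alpha 0.05, power 80% (Section 8.1; sidedness not stated). With the arcsine formula, two-sided:

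- h = 2·arcsin(√0.60) − 2·arcsin(√0.30) = 0.613
- n = (1.960 + 0.842)² / 0.613² = 20.9, rounded up to 21

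The figure reproduces. It concerns pT0 only. No sample size or null rate is given for <pT2N0 or near pCR.

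**2. The stage categories side by side (all N0).**

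| Stage at cystectomy | <pT2N0 (2.2) | pCR (7.1.1, 8.3.2.1) | near pCR (7.1.1, 8.3.3.1) |
|---|---|---|---|
| pT0 | yes | yes | no |
| pTa / pTis | yes | no | yes |
| pT1 | yes | no | no |
| pT2 or higher | no | no | no |

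pCR plus near pCR gives pT0, pTa and pTis. Since pT1N0 is missing, the sum is not <pT2N0.

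**3. Direction of the analysed rate.** Moving a patient from pT1 or higher to Ta/Tis raises near pCR; moving one from Ta/Tis to T0 lowers it. If pT0 reached the design alternative of 60%, near pCR could not exceed 100% − 60% = 40%.

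**4. Illustrative size.** Section 1.5 describes one neoadjuvant study with both rates: pT0 in 21/50 (42%), and "downstaging to <pT2 was achieved in 27 patients (54%; 95% CI, 39.3% to 68.2"%). Taking <pT2 there to include pT0, as the notation implies:

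- <pT2 but not pT0: 27 − 21 = 6 of 50 = 12% (exact 95% CI 4.5% to 24.3%)
- The Ta/Tis/T1 split of those six is not given, so near pCR lies between 0/50 and 6/50, that is 0% to 12%
- Scaled to 21 patients: <pT2 is 0.54 × 21 = 11.3, about 11; near pCR is 0 to 0.12 × 21 = 2.5, so 0 to about 3
- Exact 95% CIs: 11/21 (52%) 29.8% to 74.3%; 3/21 (14%) 3.0% to 36.3%; 0/21 0% to 16.1%

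**5. Whether the Section 8.1 null can be carried over.** Suppose <pT2N0 were put into 8.3.3.1 and the test against 30% were kept. Assume the combination adds nothing, so pT0 is 30%, and a further 12% are <pT2 but not pT0. The true <pT2N0 rate is then 42%. With X binomial on 21 patients:

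- P(X ≥ 11 | 0.30) = 0.026, so 11 or more rejects at one-sided 0.05
- P(X ≥ 11 | 0.42) = 0.23

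The test would reject about 23% of the time with no gain in pT0, because a rate that contains pT0 is being set against a pT0-only null. Near pCR does not suit this null either: at a true rate of 12%, P(X ≥ 11) is about 8 in a million.

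**The case against.** **Nothing is lost.** The endpoint is clear in 2.2, pT and pN stage come with the pathology report, and no sample size, stopping rule or decision depends on this rate. That stands, and it lowers the severity. It does not supply an analysis of the endpoint.

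**pT0 patients are reported anyway.** A reader might infer that the plan drops its best responders. It does not: 8.3.2.1 estimates and tests the pT0 rate. What remains missing is pT1N0 and the combined rate.

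**Partial response might mean <pT2 without pT0.** Section 2.2 states no such exclusion. On that reading the gap shrinks to pT1N0 alone, but 8.3.3.1 still does not analyse the endpoint.

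**Section 7.1.1 is not meant to be exhaustive.** It introduces its list as definitions of complete response, and <pT2N0 is plain staging notation. This is fair: the necessary change is in 8.3.3.1, and a new class in 7.1.1 is not essential.

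**Node-positive Ta/Tis.** A reader might infer that 8.3.3.1 would count a pTaN1 patient, because it does not repeat the nodal condition. Near pCR is already defined in 7.1.1 with negative nodes, so the omission is largely covered.

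**Conclusion.** The mismatch is real. The declared secondary endpoint is <pT2N0, the planned analysis is of Ta/Tis only, and pT1N0 is in neither planned rate. On the one available illustration, the analysed rate would be 0% to 12% where the endpoint is 54%, or 0 to about 3 of 21 patients instead of about 11. This size rests on another agent, on a <pT2 count with no stated nodal condition, and on an unknown Ta/Tis/T1 split. It is not a forecast for this trial.

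Two stronger readings are not supported. The near-pCR rate does not simply fall as treatment works better; it can move either way. Nor does the mismatch break comparison with a range of cited studies: of the neoadjuvant studies described in the introduction, only one gives a <pT2 rate.

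N = 21 and the primary pT0 analysis are unaffected. This should be fixed, but it does not threaten the trial's main conclusion.

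**What to change.** - In 8.3.3.1, replace the near-pCR rate with the <pT2N0 rate of Section 2.2: pT0, pTa, pTis or pT1, all N0.
- Use the same patients as the primary pT0N0 analysis, and name that set. Section 7.1.1 limits evaluability to patients with at least one cycle and pathology at resection, while 8.3.1 analyses everyone who received any study drug.
- Report a point estimate with an exact 95% CI. Do not test it against the Section 8.1 complete-response null. If a test is wanted, state and justify a separate null for <pT2N0.
- Keep near pCR (Ta/Tis, N0 as in 7.1.1) as a descriptive breakdown, and show pT1N0 beside it so that the parts add up to <pT2N0.

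The cost is a wording amendment. Stage data are already collected, so no new data, patients or procedures are needed.
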